6. SAFETY ANALYSIS

Safety Analysis will be performed for the Safety Population. Data from the unscheduled visits will only be listed but not tabulated.

6.1 Adverse Events

Solicited adverse events are documented in the subject diary. Serious solicited AEs are also reported in the Adverse Event Log. Unsolicited adverse events are documented in the AE log.

6.1.1 Data Points

The following information will be analyzed descriptively and corresponding details on the subject level will be provided in data listings:

- Adverse Events Overview (solicited and unsolicited AEs)
- Adverse Events Overview (solicited and unsolicited AEs) stratified by age group, region and B.b. s.l. serostatus
- Serious Adverse Events (solicited and unsolicited) by SOC and PT
- Medically attended Adverse Events (solicited and unsolicited) by SOC and PT
- Adverse Events (solicited and unsolicited) leading to withdrawal from further vaccination by SOC and PT
- Adverse Events (solicited and unsolicited) leading to withdrawal from study by SOC and PT
- Non-Serious solicited or unsolicited AE by SOC and PT for PTs with Frequency >5% in any treatment group
- Non-Serious solicited or unsolicited AE by SOC and PT for PTs with Frequency >10% in any treatment group

Solicited AE Tables (eCRF Section "Subject Diary")

- Solicited Adverse Events after any vaccination (by symptom, by maximum severity)
- Solicited Adverse Events by Vaccination Period (by symptom, by maximum severity)
- Solicited Adverse Events by Diary Day (overall and by symptom)
- Mean Duration (in days) of solicited Adverse Events
- Greatest Single Diameter (in cm) for Present Erythema, Swelling and Induration
- Body Temperature (in °C) for case of fever

Unsolicited AE Tables (eCRF Section "Adverse Event Log) for specific types of AEs (e.g. any unsolicited AE, any unsolicited SAE)

- Unsolicited Adverse Events by SOC and PT
- Unsolicited Adverse Events by Vaccination Period
- Unsolicited Adverse Event by Maximum Severity (overall and for specific types of AEs)
- Unsolicited Adverse Event by Causality (overall and for specific types of AEs)

The following figures will be provided:

- Bar chart: The number and percentage of subjects with solicited local Adverse Events by symptom and overall, by treatment group and grade for the diary period after each vaccination and for the whole treatment period.

Inferential analysis will be performed as described in Section 6.1.3**Error! Reference source not found..** Details are specified in Section 7.

6.1.2 *Derivations and Definitions*

[figure not shown]
6.1.2.1 General Principles for Analysis of Adverse Event

- In general, for tables summarizing solicited AEs, only the Subject Diary will be used. For tables for all AEs (solicited and unsolicited) in general the unsolicited AEs will be taken from the eCRF section “AE-log” and the solicited AEs will only be taken from the eCRF section “Subject Diary”.
- Tables showing “severe” events will include events with grade 3 or 4 (or missing grade).
- For tables by maximum severity and worst causality, subjects will only be counted once in highest grading category and events will be counted in each reported grading category.
- Percentages in tables that do not present data by time periods are based on N (treatment group totals).
- For the IA Day 85 all AEs from the eCRF section “Subject Diary” and AEs from the eCRF section “AE log” that started up to Day 85 (Visit4) will be analyzed. It will be stated in the table header that AEs up to Day 85 will be analyzed.
- For the IA Day 236 all AEs from the eCRF section “Subject Diary” and AEs from the eCRF section “AE log” that started up to Day 236 (Visit 6) will be analyzed. It will be stated in the table header that AEs up to Day 236 will be analyzed.
- AEs in the AE log will be considered to have started up to Day 85 if the start date of the AE is before or on study Day 85 (Visit 4). In case of an incomplete start date where it cannot clearly be decided if the AE started up to Day 85 or not, the AE will be considered to have started up to Day 85. The derivation of AEs started before or on Day 236 will be determined analogously.
- For analysis of non-serious solicited (eCRF section “Subject Diary”) and non-serious unsolicited (eCRF section “Adverse Event log”) AEs only AEs for which the question “Serious adverse event” was ticked with “no” in the eCRF will be included. Adverse Events will only be included for this analysis if their occurrence by PT in at least one treatment group in the Safety Population is 5% or over 10%, respectively.

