1.3.2 Secondary Endpoints

Immunogenicity:

- GMTs for IgG against each OspA serotype (ST1 to ST6), determined by ELISA, at Day 1, 29, 57, 180, 236, and Month 12;
- Seroconversion rates (SCRs) for each OspA serotype specific IgG (ST1 to ST6), determined by ELISA, at Day 29, 57, 85, 180, 236, and Month 12;
- Geometric Mean Fold Rise (GMFR) as compared to baseline for IgG against each OspA serotype (ST1 to ST6), determined by ELISA, at Day 29, 57, 85, 180, 236 and Month 12;
- GMTs, SCRs and GMFRs for IgG against each OspA serotype (ST1 to ST6), determined by ELISA, at Day 1, 29, 57, 85, 180, 236, and Month 12, stratified by age group.

Safety:

- Frequency of Serious Adverse Events (SAEs) during the entire study;
- Frequency of related SAEs during the entire study;
- Frequency of Adverse Events of Special Interests (AESIs) during the entire study;
- Frequency of related AESIs during the entire study;
- Frequency of unsolicited Adverse Events (AEs) during the entire study (incl. clinically relevant laboratory parameters);
- Frequency of related unsolicited AEs during the entire study (incl. clinically relevant laboratory parameters);
- Frequency of solicited local and solicited systemic AEs within 7 days after each and after any vaccination.
- Frequency of SAEs, AESIs, solicited and unsolicited AEs during the entire study stratified by age group.

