2.10 Analysis Populations

2.10.1 Safety Population

The Safety Population includes all subjects who entered into the study and received at least one vaccination. The Safety Population will be used for all safety analyses as well as demographic data. All analyses based on the Safety Population will be carried out using the actual treatment received. Subjects with vaccination errors will be allocated to a treatment group for safety analyses after a case-by-case review in the BDRM; applying the following general rules:

- If a subject received different VLA15 doses at different visits, the minimum dose received will decide the treatment group of the subject for safety analysis;
- If a subject received both VLA15 and placebo, the subject will be analyzed in a VLA15 group (dose decided by the first rule)

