6.1.2.2 Principles for Solicited Adverse Events

Solicited AEs comprise reactions at the injection site or systemic reactions that are typical for vaccinations:

- Solicited local AEs: pain, tenderness, induration/ hardening, swelling and erythema/ redness
- Solicited systemic AEs: headache, myalgia (muscle pain), arthralgia (joint pain), fever (oral body temperature), flu-like symptoms, nausea, vomiting and fatigue
- Solicited AEs are per definition regarded as related to IMP.
- For tables that summarize solicited AEs over several diary days / diary periods from the Subject Diary, the worst severity of all diary days / diary periods is taken as the events severity.
- Percentages in tables for solicited AEs by diary period /diary day are based on the number of subjects with available information (diary completed or symptom present on at least one day). In particular, if a

symptom was not assessed at a certain diary day and the symptom is reported as not present on the other days, the subject is not included in the table of the respective symptom and diary period.

- For the derivation of the duration of solicited Adverse Events by symptom and vaccination period the difference of the first occurrence and the last occurrence of the concerning event in the respective vaccination period will be taken, no matter if the event is continuous or not. Therefore, also the end-date if ongoing after day 6 will be considered. If the AE was ongoing after day 6 but has a missing or incomplete end-date, the date of last attended visit will be used as end date.
- For swelling, redness and induration, the maximum diameter per diary period in cm will be derived as taking the maximum of all diameters reported in that period for that symptom and converting via $[cm] = [in] \times 2.54$.
- The maximum body temperature per diary period for present symptom fever will be derived as taking the maximum temperature of all temperatures reported in that period and converting via $[^{\circ}C] = ([^{\circ}F] - 32) \times 5/9$.
- Adverse Events from the Subject Diary will be coded according to the table below:

[figure not shown]
Event	SOC name	SOC code	PT name	PT code
Arthralgia	Musculoskeletal and connective tissue disorders	10028395	Arthralgia	10003239
Fatigue	General disorders and administration site conditions	10018065	Fatigue	10016256
Fever	General disorders and administration site conditions	10018065	Pyrexia	10037660

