Table 14.1.4.11:	Subjects with Solicited and Unsolicited Adverse Events Leading to Withdrawal from Study by SOC and PT (Safety Population)	X	X	Including statistical test
Table 14.1.4.12:	Subjects with any Non-Serious AE by SOC and PT for PTs with Frequency >5% in any Treatment Group (eCRF Section 'AE Log' for Unsolicited AEs and 'Subject Diary' for Solicited AEs, Safety Population)	X	X	Including statistical test
Table 14.1.4.13:	Subjects with any Non-Serious AE by SOC and PT for PTs with Frequency >10% in any Treatment Group (eCRF Section 'AE Log' for Unsolicited AEs and 'Subject Diary' for Solicited AEs, Safety Population)	X	X	Including statistical test
Table 14.1.4.14:	Subjects with Solicited Adverse Events after any Vaccination (Safety Population)	X		Including statistical test
Table 14.1.4.15:	Subjects with Severe Solicited Adverse Events after any Vaccination by Symptom (Safety Population)	X		Including statistical test
Table 14.1.4.16:	Subjects with Solicited Local Adverse Events after any Vaccination by Symptom (Safety Population)	X		Including statistical test
Table 14.1.4.17:	Subjects with Solicited Local Adverse Events after any Vaccination by Symptom and Age Group (Safety Population)	X		Including statistical test
Table 14.1.4.18:	Subjects with Solicited Local Adverse Events after any Vaccination by Symptom and Region (Safety Population)	X		Including statistical test
Table 14.1.4.19:	Subjects with Solicited Local Adverse Events after any Vaccination by Symptom and B.b. s.l. serostatus (Safety Population)	X		Including statistical test
Table 14.1.4.20:	Subjects with Solicited Systemic Adverse Events after any Vaccination by Symptom (Safety Population)	X		Including statistical test
Table 14.1.4.21:	Subjects with Solicited Systemic Adverse Events after any Vaccination by Symptom and Age Group	X		Including statistical test

	(Safety Population)			
Table 14.1.4.22:	Subjects with Solicited Systemic Adverse Events after any Vaccination by Symptom and Region (Safety Population)	X		Including statistical test
Table 14.1.4.23:	Subjects with Solicited Systemic Adverse Events after any Vaccination by Symptom and B.b. s.l. serostatus (Safety Population)	X		Including statistical test
Table 14.1.4.24:	Subjects with Solicited Adverse Events after any Vaccination Classified by Maximum Severity (Safety Population)	X		Including statistical test

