Table 14.1.4.25:	Subjects with Solicited Local Adverse Events after any Vaccination by Symptom Classified by Maximum Severity (Safety Population)	X		Including statistical test
Table 14.1.4.26:	Subjects with Solicited Local Adverse Events after any Vaccination by Symptom and Age Group Classified by Maximum Severity (Safety Population)	X		Including statistical test
Table 14.1.4.27:	Subjects with Solicited Local Adverse Events after any Vaccination by Symptom and Region Classified by Maximum Severity (Safety Population)	X		Including statistical test
Table 14.1.4.28:	Subjects with Solicited Local Adverse Events after any Vaccination by Symptom and B.b. s.l. serostatus Classified by Maximum Severity (Safety Population)	X		Including statistical test
Table 14.1.4.29:	Subjects with Solicited Systemic Adverse Events after any Vaccination by Symptom Classified by Maximum Severity (Safety Population)	X		Including statistical test
Table 14.1.4.30:	Subjects with Solicited Systemic Adverse Events after any Vaccination by Symptom and Age Group Classified by Maximum Severity (Safety Population)	X		Including statistical test
Table 14.1.4.31:	Subjects with Solicited Systemic Adverse Events after any Vaccination by Symptom and Region Classified by Maximum Severity (Safety Population)	X		Including statistical test
Table 14.1.4.32:	Subjects with Solicited Systemic Adverse Events after any Vaccination by Symptom and B.b. s.l. serostatus Classified by Maximum Severity (Safety Population)	X		Including statistical test
Table 14.1.4.33:	Subjects with Solicited Adverse Events by Vaccination Period (Safety Population)	X		Including statistical test
Table 14.1.4.34:	Subjects with Solicited Local Adverse Events by Symptom and by Vaccination Period (Safety Population)	X		Including statistical test
Table 14.1.4.35:	Subjects with Solicited Systemic Adverse Events by Symptom and by Vaccination Period (Safety Population)	X		Including statistical test

Table 14.1.4.36:	Subjects with Solicited Adverse Events by Vaccination Period Classified by Maximum Severity (Safety Population)	X		Including statistical test
Table 14.1.4.37:	Subjects with Solicited Local Adverse Events by Vaccination Period Classified by Maximum Severity (Safety Population)	X		Including statistical test
Table 14.1.4.38:	Subjects with Solicited Systemic Adverse Events by Vaccination Period Classified by Maximum Severity (Safety Population)	X		Including statistical test

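### Solicited AE rates after any vaccination are divided by all vaccinated subjects, so subjects with no diary data count as reaction-free, while the by-period rates of the same endpoint use only subjects with diary information

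*SAP*

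**What the plan says.** The secondary safety endpoint in SAP Section 1.3.2 asks for two kinds of rate: "Frequency of solicited local and solicited systemic AEs within 7 days after each and after any vaccination". The SAP sets a different denominator for each.

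- **After any vaccination.** Section 6.1.2.1: "Percentages in tables that do not present data by time periods are based on N (treatment group totals". Tables 14.1.4.14 to 14.1.4.32, beginning with "Subjects with Solicited Adverse Events after any Vaccination (Safety Population", are not split by time period and fall under this rule. For safety tables N is the Safety Population, defined in Section 2.10.1: "The Safety Population includes all subjects who entered into the study and received at least one vaccination". No diary is required.
- **After each vaccination and by diary day.** Section 6.1.2.2: "Percentages in tables for solicited AEs by diary period /diary day are based on the number of subjects with available information". Tables 14.1.4.33 to 14.1.4.43, beginning with "Subjects with Solicited Adverse Events by Vaccination Period (Safety Population", fall under this rule. If a symptom was not assessed on some day and was absent on the others, "the subject is not included in the table of the respective symptom and diary period".

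The numerator has one source for both. Section 6.1.2.1: "In general, for tables summarizing solicited AEs, only the Subject Diary will be used".

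Two general rules bear on the point. Section 2.5 makes non-missing observations the default basis for percentages unless something else is stated. Section 2.7 applies a worst-case approach to missing attributes of an AE, such as seriousness or severity, and does not address a diary with no data.

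**The concern.** A vaccinated subject who returns no diary data cannot contribute a solicited event but remains in N. The any-vaccination tables therefore treat missing reactogenicity data as absence of a reaction. The by-period tables leave the same subject out. The two halves of one endpoint rest on different populations, and the SAP neither reconciles them nor asks for the number of subjects without diary data beside the rates.

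The any-vaccination rates are a main summary of reactogenicity per dose. They carry 95% confidence intervals and between-group exact tests (Section 6.1.3; the comments in Section 7.1.4), in a trial that compares doses before Phase 3. A downward bias in these rates makes a dose look better tolerated than the data show. If diary return differs between groups, part of a group difference, or part of its absence, would be an artefact of the denominator.

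**Working it through.** **Nothing to reproduce.** The SAP states no solicited AE rate and no diary completion rate. The check applies the two stated rules to assumed counts.

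**Inputs.** N = 30 + 180 = 210 per selected dose (Sections 1.2 and 1.4). The number without any diary data (k), the reaction rates and the numbers of first-time reactors are assumptions.

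**1. Bias of the any-vaccination rate.** If subjects without a diary react at the same rate r as the others, the displayed rate is r × (N − k)/N. With r = 70%:

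| k of 210 | Calculation | Displayed |
|---|---|---|
| 2 | 0.70 × 208/210 | 69.3% |
| 5 | 0.70 × 205/210 | 68.3% |
| 10 | 0.70 × 200/210 | 66.7% |

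More generally, the shortfall is k/N times the reaction rate among the subjects without a diary. It is zero only if none of them reacted.

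**2. Unequal diary return.** With a true rate of 60% in two groups, 2% loss in one and 10% in the other give 0.60 × 0.98 = 58.8% and 0.60 × 0.90 = 54.0%. The 4.8-point difference is entirely an artefact.

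**3. Any-dose rate against dose-1 rate.** Let D subjects have dose-1 diary information, x react after dose 1, and y react for the first time after dose 2 or 3. The SAP compares x/D with (x + y)/N. The any-dose rate is the lower one when y < x × (N − D)/D. Take N = 210, D = 200 (the other 10 without any diary) and x = 140:

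- Dose 1: 140/200 = 70.0%.
- Threshold: 140 × 10/200 = 7 first-time reactors.
- y = 2: 142/210 = 67.6%, a reversal.
- y = 7: 147/210 = 70.0%, no reversal.

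With the same 10 subjects missing, the thresholds at dose-1 rates of 30%, 50% and 90% are 3, 5 and 9.

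**4. The by-period rate also moves.** Suppose 100 of 200 subjects with a diary react: 50.0%. If 10 partly assessed non-reactors are dropped under Section 6.1.2.2, the rate is 100/190 = 52.6%. On N it is 100/210 = 47.6%. Part of any gap between the tables comes from this exclusion, not from the use of N.

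**5. With the common diary basis.** In the example of step 3 with y = 2, the rates become 140/200 = 70.0% after dose 1 and 142/200 = 71.0% after any dose.

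**The case against.** The strongest reply is that this is a stated convention. The SAP says which denominator applies to which kind of table, and dividing an any-dose rate by all vaccinated subjects is common. That is fair: the two sections do not contradict each other. A convention that codes missing diaries as no reaction still needs a reason, however, when the by-period rule for the same endpoint and the default in Section 2.5 both use available data.

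The other replies are these:

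- **Size.** All magnitudes are assumed. Only subjects with no diary at all count as wholly reaction-free, and the schedule notes provide for collecting unreturned diaries at early termination. With 2 of 210 missing, the effect at a 70% rate is 0.7 points. This stands.
- **Unequal loss.** Subjects are blinded, and the SAP gives no evidence that diary return will differ by group. This stands; the distortion between groups is conditional.
- **Reversal.** A reader might infer that the any-dose rate will fall below the dose-1 rate, or that a common denominator rules this out. The document supports neither. Step 3 shows that a few first-time reactors prevent it. It can also persist after the change: if all 210 have at least one diary but only 190 have dose-1 information, 133/190 = 70.0% after dose 1 stands against 140/210 = 66.7% after any dose.
- **Overview tables.** Changing only the solicited rows of Table 14.1.4.1 could make any solicited AE, at 180/200 = 90.0%, exceed any AE, at 185/210 = 88.1%. This stands and limits the fix.
- **Existing transparency.** Section 2.5 calls for numbers of non-missing observations, and Listing 16.2.1.4.1.19 shows solicited AEs with missing assessments. Neither changes the denominator of the percentages, intervals and tests.

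**Conclusion.** The point holds in a limited form. For the dedicated solicited AE tables after any vaccination, and the figures that show the same rates, the stated denominator counts vaccinated subjects without diary data as non-reactors and biases the rate downward. The relative size equals the no-diary share, if those subjects react like the rest: 0.7 to 3.3 points on a true 70% for 2 to 10 missing of 210. Groups are affected unequally only if diary return differs. An any-dose rate below the dose-1 rate is a possible symptom, not a predicted result. These are secondary safety rates and the primary immunogenicity analysis is untouched, but the change is small and worth making.

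**What to change.** Add one sentence to Section 6.1.2.1 or 6.1.2.2. For Tables 14.1.4.14 to 14.1.4.32 and Figures 14.1.4.1 to 14.1.4.4 and 14.1.4.6 to 14.1.4.9, percentages, confidence intervals and tests should use vaccinated subjects with diary information for at least one vaccination, or with the symptom present on at least one day. Print that n and the number of vaccinated subjects without diary data in each table and figure.

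Keep N for every row of the overview tables (14.1.4.1 to 14.1.4.4), so that any solicited AE cannot exceed any AE, and add a footnote with the number without diary data.

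The cost is the sentence, a denominator flag and footnotes. The downside is that the solicited rate in the overview and in the dedicated tables will have different denominators. A small reversal against the dose-1 rate can also remain when only the dose-1 diary is missing or partial; the printed n lets the reader see why.

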6.1.2.2 Principles for Solicited Adverse Events

Solicited AEs comprise reactions at the injection site or systemic reactions that are typical for vaccinations:

- Solicited local AEs: pain, tenderness, induration/ hardening, swelling and erythema/ redness
- Solicited systemic AEs: headache, myalgia (muscle pain), arthralgia (joint pain), fever (oral body temperature), flu-like symptoms, nausea, vomiting and fatigue
- Solicited AEs are per definition regarded as related to IMP.
- For tables that summarize solicited AEs over several diary days / diary periods from the Subject Diary, the worst severity of all diary days / diary periods is taken as the events severity.
- Percentages in tables for solicited AEs by diary period /diary day are based on the number of subjects with available information (diary completed or symptom present on at least one day). In particular, if a

symptom was not assessed at a certain diary day and the symptom is reported as not present on the other days, the subject is not included in the table of the respective symptom and diary period.

- For the derivation of the duration of solicited Adverse Events by symptom and vaccination period the difference of the first occurrence and the last occurrence of the concerning event in the respective vaccination period will be taken, no matter if the event is continuous or not. Therefore, also the end-date if ongoing after day 6 will be considered. If the AE was ongoing after day 6 but has a missing or incomplete end-date, the date of last attended visit will be used as end date.
- For swelling, redness and induration, the maximum diameter per diary period in cm will be derived as taking the maximum of all diameters reported in that period for that symptom and converting via $[cm] = [in] \times 2.54$.
- The maximum body temperature per diary period for present symptom fever will be derived as taking the maximum temperature of all temperatures reported in that period and converting via $[^{\circ}C] = ([^{\circ}F] - 32) \times 5/9$.
- Adverse Events from the Subject Diary will be coded according to the table below:

[figure not shown]
Event	SOC name	SOC code	PT name	PT code
Arthralgia	Musculoskeletal and connective tissue disorders	10028395	Arthralgia	10003239
Fatigue	General disorders and administration site conditions	10018065	Fatigue	10016256
Fever	General disorders and administration site conditions	10018065	Pyrexia	10037660
Flu like symptom	General disorders and administration site conditions	10018065	Influenza like illness	10022004
Headache	Nervous system disorders	10029205	Headache	10019211
Myalgia	Musculoskeletal and connective tissue disorders	10028395	Myalgia	10028411
Nausea	Gastrointestinal disorders	10017947	Nausea	10028813
Vomiting	Gastrointestinal disorders	10017947	Vomiting	10047700
Erythema/Redness	General disorders and administration site conditions	10018065	Injection site erythema	10022061
Induration/Hardening	General disorders and	10018065	Injection site	10022075

	administration site conditions		induration	
Pain	General disorders and administration site conditions	10018065	Injection site pain	10022086
Swelling	General disorders and administration site conditions	10018065	Injection site swelling	10053425
Tenderness	General disorders and administration site conditions	10018065	Injection site pain	10022086

